230 subjects total (100 each group). This extra 30 subjects will allow for screen failures that occur on the study for example change in plans from use of ETT or LMA to nasal cannula in the procedure room after subjects may have been consented. They will not be randomized and need to be replaced on the study.

2. What is the statistical or other justification for the total number of subjects described above?

Sample sizes of 75 per group achieve 80% power to detect a difference of 2 mmHg between the null hypothesis that both group mean EtCO₂ measurement over the length of the monitoring period are 37.2 mmHg and the alternative hypothesis that the mean of the CO₂ group is 39.2 with an estimated within group standard deviation of 4.3 mmHg and with a significance level (alpha) of 0.05 using a two-sided two-sample t-test. To adjust for the possibility of a 25% drop out rate 100 patients per group will be enrolled.

We have also allowed 30 extra subjects due to some screen failures we have had.

5. Gender of the Subjects

A. Are there any enrollment restrictions based on gender?

No

6. Age Range of Subjects

A. Will adults be enrolled ?

Yes

1. What is the age range of the adult subjects?

The adults in this study will be 19 years old.

2. What is the rationale for selecting this age range?

As we were enrolling subjects into this study we noticed we had several 19 year old subjects still being seen by our GI Department. Therefore, they would qualify for the study. We did

not want to exclude them from participating in the study. The research will be conducted in children aged 6 months to 19 years to determine if end tidal CO₂ remains persistently elevated in intubated children undergoing upper endoscopy with CO₂ insufflation and to determine if there are changes in minute ventilation with CO₂ use during upper endoscopy.

B. Will children (18 years of age or younger) be included in this research?

Yes

1. What is the justification for inclusion of children in this research?

The research will be conducted in children aged 6 months to 18 years to determine if end tidal CO₂ remains persistently elevated in intubated children undergoing upper endoscopy with CO₂ insufflation and to determine if there are changes in minute ventilation with CO₂ use during upper endoscopy.

2. What is the age range for the child subjects, and what is the justification for selecting this age range?

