After it has been determined that the patient can be included in the study and the consents have been signed; the procedure nurse will open the first envelope and randomly pick either CO₂ or Air. She will then set up the insufflation gas based on the gas picked. She will cover the air and CO₂ dispensing machine so that the patient, anesthesiologist and endoscopist are all blinded to the type of insufflation gas used during the procedure. She will complete randomization using the cards in each set of envelope before moving to the next set. The endoscopy room/procedure room nurse will keep a record of patients randomized into the air or CO₂ group in a locked cabinet. She will assign arbitrary letters or numbers to the gas used so that the biostatistician who will perform the interim analysis will be blinded to the arm of

study as well.

- Data including age, gender, weight z scores, BMI, co-morbid factors and reason for endoscopy will be collected on all children enrolled in the study. Name and level of expertise of the endoscopist will be collected including the duration of both the procedure and anesthesia and any procedural or anesthesia related complications encountered during the procedure or within forty-eight hours of the procedure.
- Vital signs including heart rate, respiratory rate, blood pressure, end tidal CO₂ level and minute ventilation (tidal volume x respiratory rate) will be recorded before the procedure and continuously monitored during the procedure as per anesthesia protocol.
- Information regarding end tidal CO₂ level and minute ventilation will be recorded for both groups and compared to the pre-procedure values. We will also collect data on the type of anesthetic medications used and the presence of any of these symptoms (nausea, vomiting or headaches) after the procedure. Please also see attached flow chart below for protocol and randomization.

C. Select any of the following that apply to the research:

Phase I study

♦ Randomization

Placebo (or non-treatment arm)

Washout

Sensitive surveys or questionnaires

None of the above

Describe randomization process and schedule

This is a double blinded , randomized clinical study. Both the endoscopist and patients will be blinded to the insufflation gas used; Air or CO₂. The procedure room/ endoscopy room nurse will then randomize the patients as described below:

The nurse will receive 4 envelopes.

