Continuous data will be reported as means with standard deviations, or medians with interquartile ranges depending if variable has normal or skewed distribution respectively. Categorical variables will be described by percentages and proportions. Comparisons of continuous data will be performed using the t-test or Wilcoxon signed-ranks test. Categorical variables will be compared using the chisq test or Fishers exact test. A probability value <.05 will be considered significant. Statistical analysis will be performed using SAS 9 statistical software (SAS Institute, Cary, NC) or Graph Pad Prism 7 for Windows (Graph pad Software, San Diego, CA).

Descriptive statistics, including counts and %, means, SD, medians, will be used to summarize patient characteristics, procedural, anesthesia and safety outcomes for the two groups. Patient characteristics, Patient safety outcomes;(MV, EtCO₂), procedural, and anesthesia outcomes will be compared between the groups using the independent sample t-test or Mann-Whitney test or Fishers exact test as appropriate to the data. Changes in these safety outcome measurements across the monitoring period between the two groups using a mixed effects model will be considered

F. Does this study involve the collection of blood, urine, saliva or other human biological material (HBM)?

No

DRUGS, BIOLOGIC DRUGS AND DEVICES

13. Drugs and Biologic Drugs

1. Does this research involve the use of drugs or biologics?

No

14. Devices

1. Does this research involve a medical device(s)?

No

CONFIDENTIALITY AND PRIVACY

15. Confidentiality and Privacy

A. Describe where research data will be stored. Check all that apply.

♦ On a secure server at UNMC, CHMC, Nebraska Medicine, and/or UNO (including REDCap)

On a secure cloud server - Specify the secured cloud serve:

On a firewall protected database accessible through the internet - Specify who has administrative responsibility for maintenance of the server:

On an encrypted, password protected local hard drive

On an encrypted, password protected portable computer

On an encrypted, password protected flash drive

♦ In hard copy

♦ Other Hard copies of the original signed consent and assent forms will be stored in a locked file cabinet, or in a lock briefcase when not in use

a. Please provide justification for use of hard copies

Hard copies of consent and assent are required and are kept as per institutional policy.

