Previous studies in adults have documented safety and efficacy of CO₂ for insufflation in decreasing abdominal distension and discomfort. Patients will be continuously monitored throughout the procedure. If there is any evidence of respiratory distress or other potential CO₂ complications, the endoscopist will be unblinded; and CO₂ will be turned off if it is being used. Physicians will be immediately available throughout the procedure and prior to discharge from the procedure suite. They will also be available by [contact].

B. Describe how the data collected will be monitored to ensure the safety of subjects.

Identify who will perform the ongoing data and safety analysis, and describe the frequency of data analysis. If there is an independent Data and Safety Monitoring Board (DSMB) provide the charter, or describe (1) the composition of the DSMB membership, (2) the frequency of DSMB meetings and reports.

An interim safety analysis will occur after enrollment of the first half of the subjects are enrolled; 50 subjects in the GA group and 50 subjects in the MAC group. The principal investigator and co-investigators will take part in this analysis.

C. Describe the auditing plan for research conducted. Identify who will conduct the

audits and specify the audit frequency.

The principal investigator will conduct auditing of the data after every 50 subjects enrolled in the study.

D. Describe the specific subject withdrawal criteria.

If any potential risks is observed during the procedure such as with evidence of respiratory distress or other potential CO₂ complications, the endoscopist will be unblinded; and CO₂ will be turned off if it is being used and the subject will be withdrawn from the study.

E. Describe the stopping rules for the research (e.g., the specific criteria for halting or early termination of the study).

The research will be terminated early if there are significant reports of adverse events reported in an arm of the study. It will also be stopped early if significant results are reported during the interim analysis after enrollment of the first half of the subjects are enrolled. .

F. Describe plans and resources available to promptly address any subject injury.

Physicians will be immediately available throughout the procedure and prior to discharge from the procedure suite. They will also be available by [contact].

19. Potential Benefits to the Subject

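### Item 18.D withdraws randomised subjects after a possible CO₂ complication, and no text says their EtCO₂ readings are analysed in the randomised arm

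*Combined protocol and SAP*

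**What the plan says.** **Withdrawal rule.** Item 18.D opens with a broad trigger, given by example and without an EtCO₂ threshold: "If any potential risks is observed during the procedure such as with evidence of respiratory distress or other potential CO₂ complications". The endoscopist is then unblinded, and "CO₂ will be turned off if it is being used and the subject will be withdrawn from the study". The event occurs during the procedure, so after randomisation, and the rule covers both arms. Item 18.A describes unblinding and gas-off for the same event and does not mention withdrawal.

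**Data collected.** Item 12.B has EtCO₂ and MV recorded before the procedure, monitored continuously during it, and compared with the pre-procedure values in both groups. It also lists "any procedural or anesthesia related complications encountered during the procedure or within forty-eight hours of the procedure". Item 18.E acts on adverse events by arm: "The research will be terminated early if there are significant reports of adverse events reported in an arm of the study".

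**Analysis.** Item 12.E says "Patient safety outcomes;(MV, EtCO₂), procedural, and anesthesia outcomes will be compared between the groups", using a t-test, Mann-Whitney test or Fisher's exact test. It adds: "Changes in these safety outcome measurements across the monitoring period between the two groups using a mixed effects model will be considered". It gives no analysis set and no rule for withdrawn subjects.

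**Sample size.** Item 4 sizes the trial on mean EtCO₂ over the monitoring period and says "To adjust for the possibility of a 25% drop out rate 100 patients per group will be enrolled". Thirty further subjects cover screen failures, of whom it says "They will not be randomized and need to be replaced on the study".

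**The concern.** A subject removed under 18.D leaves because of something that happened after randomisation and that plausibly relates to EtCO₂ or MV, the outcomes being compared. If such subjects are also dropped from the analysis, the remaining groups are no longer the randomised groups.

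The likely lean matters here. The hypothesis in item 3 is that protecting the airway removes the EtCO₂ elevation. If withdrawals are commoner with CO₂, and withdrawn subjects run similarly higher EtCO₂ in both arms, excluding them moves the estimate toward that reassuring answer. Item 20 attaches a practice consequence to the result. Enrolling more subjects restores precision but does not correct selective loss.

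**Working it through.** **1. The plan's own figure.** Inputs from item 4: difference 2 mmHg (39.2 against 37.2), SD 4.3 mmHg, two-sided alpha 0.05, power 80%.

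- Normal approximation: n = 2 × (1.960 + 0.842)² × 4.3² / 2² ≈ 73 per group.
- Noncentral t: 74 per group gives 80.2% power and 75 gives 80.8%. The stated 75 reproduces.
- Drop-out: 75 / (1 − 0.25) = 100 per group, as stated. With all 100 analysed, power is 90.5%.

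**2. Sign of the bias if withdrawn subjects are left out.** Let p be the share withdrawn in an arm, and d the mean EtCO₂ of withdrawn minus retained subjects in that arm.

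Bias in (CO₂ − air) = −(p₁d₁ − p₀d₀), with 1 = CO₂ and 0 = air.

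- p₁ = 5%, p₀ = 1%, d = 4.3 in both arms: −(0.215 − 0.043) = −0.17 mmHg.
- p₁ = p₀ and d₁ = d₀: zero.
- p₁ = 5%, d₁ = 2; p₀ = 2%, d₀ = 8: −(0.10 − 0.16) = +0.06 mmHg. Withdrawals are commoner with CO₂ and go with higher EtCO₂ in both arms, yet the bias is upward. The condition is therefore on rate times excess, not on rate alone.

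**3. Size under a simple model.** Assumptions, none from the documents: 100 per arm before withdrawal and no other loss; withdrawal removes the upper tail of a latent normal score that has correlation rho with the patient's mean EtCO₂; the same rho in both arms.

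Shift in an arm's retained mean = −4.3 × rho × φ(c) / (1 − p), where c is the normal quantile at 1 − p.

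Example, 5% against 1%, rho 0.5:

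- CO₂: c = 1.645, φ = 0.1031, shift = −4.3 × 0.5 × 0.1031 / 0.95 = −0.2334.
- Air: c = 2.326, φ = 0.0267, shift = −4.3 × 0.5 × 0.0267 / 0.99 = −0.0579.
- Expected difference: 2 − 0.2334 + 0.0579 = 1.82 mmHg.

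Expected difference in mmHg when the true difference is 2, with power from a Welch t-test in brackets:

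| Withdrawn, CO₂ / air | rho 0.2–0.3 | rho 0.5–1.0 |
|---|---|---|
| 1% / 0% | 1.97–1.98 (90%) | 1.88–1.94 (88–89%) |
| 2% / 1% | 1.97–1.98 (90%) | 1.90–1.95 (89–90%) |
| 5% / 1% | 1.89–1.93 (87–88%) | 1.65–1.82 (81–85%) |
| 10% / 1% | 1.78–1.86 (81.5–84%) | 1.28–1.64 (61–76%) |
| 5% / 5% | 2.00 | 2.00 |
| 1% / 5% | 2.07–2.11 | 2.18–2.35 |

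At rho 0 the difference is 2.00 in every row. A simulation of the 5% / 1% row gave 1.89, 1.83 and 1.65 at rho 0.3, 0.5 and 1.0, in agreement.

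If the correlation differs by arm, 5% at rho 0.2 with CO₂ against 2% at rho 0.7 with air gives 2 − 0.093 + 0.149 = 2.06 mmHg, again upward.

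**4. True difference zero, as hypothesised.** With 5% against 1%, the expected difference is −0.07 to −0.11 mmHg at rho 0.2–0.3 (two-sided false-positive rate 5.1–5.3%) and −0.18 to −0.35 mmHg at rho 0.5–1.0 (6.0–9.3%).

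**The case against.** The strongest reply is that exclusion is inferred, not written. Item 12.B collects EtCO₂, MV and complications; 18.A handles the same event without withdrawal; and item 11 says the study takes place only during the procedure. Item 18.D can therefore be read as ending the study intervention, with the recorded readings kept. That is a fair reading, and it is why the bias is stated only conditionally. It does not close the point: collecting data is not a rule for analysing them, and 18.A and 18.D do not agree.

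The reply is also right that the larger biases rest on assumptions that no document supports. Rho of 1.0 makes withdrawal a direct function of mean EtCO₂, which does not fit a trigger as broad as 18.D's. Item 10 excludes chronic respiratory disease, cyanotic heart disease and ASA 3 or above, so events may be rare.

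Four stronger inferences are tempting and should not be drawn:

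- That the drop-out allowance shows withdrawn subjects are excluded. Item 4 neither defines drop-out nor refers to 18.D.
- That 34% against 4% in item 16 predicts withdrawal. Those figures are EtCO₂ above 60 mmHg in non-intubated patients, not withdrawals.
- That complications will be undercounted with CO₂. Items 12.B and 18.E point toward their being counted.
- That exclusions will be chosen by arm. Item 32.C keeps the arms masked until the analysis is done, although this does not define who is analysed.

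**Conclusion.** The point holds in a conditional form. Item 18.D takes a randomised subject out of the study for an event related to the compared outcomes, and no text puts that subject's readings back into the randomised comparison.

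A reader might infer that the plan does exclude these subjects, or that the result must lean toward no elevation. The documents support neither. The direction is downward only if rate times excess EtCO₂ is larger with CO₂.

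With equal correlation in both arms, the bias is about 0.1 mmHg or less of 2 mmHg at 1–2% CO₂-arm withdrawal, and about 0.1 mmHg at 5% against 1% with low correlation. It reaches about 0.2 mmHg or more with roughly 5% or more withdrawn in the CO₂ arm and a correlation of 0.5 or more. At 10% against 1% it is already 0.14–0.22 mmHg at rho 0.2–0.3. No withdrawal rate or correlation is given, so none of these figures is a forecast. No direction is claimed for MV. This is a cheap improvement, not a flaw that invalidates the design.

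**What to change.** Leave the clinical response as it is, and separate stopping the gas from leaving the dataset:

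- Reconcile 18.A with 18.D on whether gas-off means leaving the study.
- In 18.D, state that EtCO₂, MV and complication data from routine monitoring of such a subject are retained.
- In 12.E, state that all randomised subjects with any EtCO₂ recording are analysed by randomised arm.
- Report unblinding and gas-off events by arm.
- Add a sensitivity analysis using EtCO₂ and MV readings up to gas-off (CO₂ arm) or unblinding (air arm).

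**Cost.** A sentence in 18.D and two or three in 12.E. Monitoring is already continuous, so no new measurement is needed and the sample size is unchanged. The consent form, which was not available for this review, may need a line on data retention.

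**Downside.** Readings after gas-off dilute the contrast. If the whole 2 mmHg effect vanished at gas-off and 5% of the CO₂ arm had the gas off for a share f of monitoring, the difference would be 2 × (1 − 0.05 × f): 1.95 mmHg at f = 0.5 and 1.90 at f = 1. That is similar to the exclusion bias at 5% / 1% with rho 0.2–0.3 and smaller than at 0.5–1.0. The sensitivity analysis shows how much it matters.

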Each envelope will contain 25 cards marked "Air" and 25 cards marked "CO2" ; Therefore, there will be a total of 100 cards marked "Air" and 100 cards marked "CO2" in all the 4 sets of envelopes

After it has been determined that the patient can be included in the study and the consents have been signed; the procedure nurse will open the first envelope and randomly pick either CO₂ or Air. She will then set up the insufflation gas based on the gas picked. She will cover the air and CO₂ dispensing machine so that the patient, anesthesiologist and endoscopist are all blinded to the type of insufflation gas used during the procedure. She will complete randomization using the cards in each set of envelope before moving to the next set. The endoscopy room/procedure room nurse will keep a record of patients randomized into the air or CO₂ group in a locked cabinet. She will assign arbitrary letters or numbers to the gas

used so that the biostatistician who will perform the interim analysis will be blinded to the arm of study as well.

We will perform an interim analysis after enrolling 100 patients (50 patients in the Air group and 50 patients in the CO₂ group)

D. Identify:

1. All procedures, interventions, evaluations and tests performed solely for research purposes (eg, administration of an investigational drug or a new psychological assessment instrument; randomization)

The consenting process for the study is only done for research purposes. Also, the only other procedures that would be performed solely for research purposes is the randomization of enrolled patients to air or CO₂ gas for insufflation during the endoscopic procedure. Although, air is the standard insufflation agent for endoscopy in pediatrics; many centers now routinely use carbon dioxide given the vast data in adults showing decreased abdominal discomfort and distension with carbon dioxide use.

In our center, we routinely use CO₂ for colonoscopy and most endoscopists use air for upper endoscopy.

2. All procedures, interventions, evaluations and tests performed for clinical indication but more frequently than they would be if the subject was not participating in the research (eg, extra blood tests; additional radiology exams)

There will be no extra blood tests or additional radiology exams

E. Describe briefly the statistical methods used to analyze the data (or reference the appropriate section of the detailed protocol or grant).

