Is there the prospect for direct benefit (eg, research on diagnosis or treatment of disease)?

Yes

Describe potential benefits to the subjects that may reasonably be expected from participation in the research, if any. If there are therapeutic and non-therapeutic components of the research, address anticipated benefits to subjects that may reasonably be expected from each of these components.

Patients randomized to the CO₂ arm may benefit from less procedure pain when used during colonoscopy as a few pediatric studies have shown these benefits with the use of CO₂ for colonoscopy.

20. Potential Benefits to Society

Describe the potential benefits to society that may reasonably be expected to result from this research.

Publishing this work may encourage the use of safe and best insufflation practices in all children. If elevated end tidal CO₂ levels persist despite protection of the airway, then CO₂ use in children may be limited or restricted to only colonoscopy.

ALTERNATIVES TO PARTICIPATION

21. Alternatives to Participation

1. Describe the likely care the subject would receive at this institution were he/she not to participate in the research. If there are more than one reasonable courses of treatment briefly describe.

There is currently no standard of care at this institution regarding use of "CO₂" versus "air" as the insufflation gas. The gas of choice to be used is usually at the discretion of the endoscopist and the availability of carbon dioxide gas in the procedure room or OR.

2. Is the potential benefit of the research at least as good as the potential benefits of the alternatives described above?

Yes

3. Are there any reasonably available alternatives outside this institution which would have the potential for providing benefit to the subjects outside the research context?

No

4. Would any of the study procedures or courses of treatment in the protocol be available to the subject if they elected not to participate?

Yes

a. Explain.

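### The half-way stop for significance names no endpoint or threshold; applying the plan's only threshold (p<.05) to mean EtCO₂ at both looks gives about 8.3% type I error, not 5%.

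*Combined protocol and SAP*

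**What the plan says.** - **Stopping rule (18.E).** There are two separate triggers. One concerns adverse events in an arm. The other is: "It will also be stopped early if significant results are reported during the interim analysis after enrollment of the first half of the subjects". No endpoint, test, direction or threshold is attached to the second.
- **Threshold (12.E).** The only definition of significance is: "A probability value <.05 will be considered significant". Nothing there, or elsewhere, adjusts for an interim look.
- **Sample size (4.A.2).** The calculation is for mean EtCO₂, with a "significance level (alpha) of 0.05 using a two-sided two-sample t-test". It assumes 75 evaluable per group, a 2 mmHg difference and an SD of 4.3 mmHg. Dropout is then added: "To adjust for the possibility of a 25% drop out rate 100 patients per group will be enrolled".
- **Timing (12.C).** "We will perform an interim analysis after enrolling 100 patients (50 patients in the Air group and 50 patients in the CO₂ group").
- **Interim groups.** In 12.B and 12.C the nurse will "assign arbitrary letters or numbers to the gas used so that the biostatistician who will perform the interim analysis will be blinded", so the comparison is between gases. In 18.B the same half-way analysis is called a safety analysis of "50 subjects in the GA group and 50 subjects in the MAC group".

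**The concern.** The plan claims a 5% error rate for one test but adds a mandatory early stop that depends on the outcome. With nothing pre-specified, whoever runs the interim must either use the unadjusted p<.05 or choose a rule once the data are in view. 18.B says the principal investigator and co-investigators take part in that analysis, and it describes no independent board.

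The result is meant to influence practice. Section 20 says that if raised EtCO₂ persists despite airway protection, "then CO₂ use in children may be limited or restricted to only colonoscopy". A chance or exaggerated difference at half-way could end the trial and feed that conclusion.

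**Working it through.** **Inputs.** Two-sided alpha 0.05, difference 2 mmHg, SD 4.3 mmHg, 75 evaluable and 100 enrolled per group, 25% dropout (4.A.2); interim at 50 per group (12.C); p<.05 (12.E). Assumption: p<.05 is applied to mean EtCO₂ at both looks.

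**1. The plan's own figure.** n per group = 2(1.960 + 0.842)² × 4.3² / 2² = 72.6, so 73; the exact t-test needs 74. Power at 75 per group is 81.3% (normal approximation) or 80.8% (t-test). Dropout: 75 / 0.75 = 100. The stated sample size reproduces.

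**2. Type I error with two looks.** Under the null, the interim and final statistics Z₁ and Z₂ are bivariate normal with correlation √t, where t is the information fraction. Type I error = 1 − P(|Z₁| < 1.96 and |Z₂| < 1.96).

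| Information fraction t | How it arises | Two-sided type I error |
|---|---|---|
| 0.40 | sensitivity value | 8.6% |
| 0.50 | 50 then 100 per arm, or about 38 then 75 with 25% dropout at both looks | 8.3% |
| 0.67 | 50 then 75 per arm | 7.7% |

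Simulated two-look t-tests (200,000 null trials per design) gave 8.3% to 8.4% at 38 then 75 and at 50 then 100 per arm. By symmetry, a false finding that CO₂ raises EtCO₂ occurs in 8.3 / 2 = about 4.2% of trials, against a nominal 2.5%.

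**3. Difference that triggers a stop.** Standard error = 4.3 × √(2/n).
- Planned dropout: 50 × 0.75 = 37.5, taken as 38 per arm. SE = 0.986; times the t critical value 1.993, this is 1.97 mmHg.
- No dropout, 50 per arm: SE = 0.860; times 1.984, this is 1.71 mmHg.

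**4. Exaggeration after a stop.** With a true difference of 1 mmHg (400,000 simulated t-tests):
- 38 per arm: 16.9% stop for higher EtCO₂ on CO₂, mean estimate 2.46 mmHg.
- 50 per arm: 20.9% stop in that direction, mean estimate 2.17 mmHg.

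These are not false positives, since the assumed difference is real. They show the reported effect more than doubled.

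**5. Boundaries that hold 5%** (same bivariate normal, solved numerically).

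| Boundary | t | Interim p | Final p |
|---|---|---|---|
| O'Brien-Fleming | 0.50 | 0.0052 | 0.048 |
| O'Brien-Fleming | 0.67 | 0.014 | 0.045 |
| Pocock | 0.50 | 0.029 | 0.029 |

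**6. Power and early stopping at a true 2 mmHg** (normal approximation, 38 then 75 per arm).

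| Rule | Power | Interim stop |
|---|---|---|
| Single look at .05 | 81.3% | none |
| p<.05 at both looks | 83.3% | 53% |
| O'Brien-Fleming | 81.0% | 23% |
| Pocock | 77.1% | 44% |

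At 50 per arm the interim stop is 64% with p<.05 and 32% with O'Brien-Fleming.

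**The case against.** **No rule is actually written.** The plan never says that p<.05 governs the interim, so the 8.3% describes one reading of an undefined rule. That is correct, and the figure is stated conditionally. It is still the only threshold the plan supplies, and leaving the rule undefined is itself a defect.

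**It is a safety interim, where a low bar for stopping can be legitimate.** 18.B does use the safety label, but 12.E lists EtCO₂ and minute ventilation as the safety outcomes, so the label does not keep the powered endpoint out. 18.E also lists significant results separately from adverse events. A deliberate lean towards early stopping could be defended, but the protocol does not state one.

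**The 8.3% overstates the feared error.** It is two-sided and cumulative. Under the null the interim alone stops 5% of trials, 2.5% in the direction of higher EtCO₂ on CO₂. This stands as a matter of reading the number; the one-directional error over both looks is still about 4.2% rather than 2.5%.

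**A stricter boundary has costs.** This also stands. At a true 2 mmHg and 38 per arm, expected enrolment rises from 200 − 100 × 0.527 = 147 to 200 − 100 × 0.226 = 177, about 30 more patients. At 50 per arm it rises from 200 − 64.3 = 136 to 200 − 31.9 = 168. An O'Brien-Fleming stop is also more inflated when it occurs. With a true 1 mmHg and 38 per arm, the mean estimate is about 1 + 0.986 × 2.18 = 3.15 mmHg, where 2.18 is the normal density over the upper tail at 2.797 − 1/0.986. Such stops are much rarer, about 4% against 17%, so average bias over all trials falls.

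**Conclusion.** The concern holds and should be settled before interim data are seen. 18.E requires a stop on an undefined criterion. Under the only threshold the plan offers, applied to the outcome used for the sample size, the two-sided type I error is 8.3% at half information (7.7% at two thirds), not the claimed 5%. This rests on one endpoint, p<.05 at both looks, and interim and final statistics that behave as in the planned t-test. If minute ventilation or other outcomes could also trigger the stop, the rate would be higher by an amount the documents do not fix. The GA/MAC wording in 18.B looks like a drafting slip and does not change the calculation, but it contradicts 12.C on which groups are compared.

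**What to change.** 1. In 12.E and 18.E, name the interim endpoint (mean EtCO₂, the sample-size outcome) and a threshold that keeps 5% overall. O'Brien-Fleming is one choice: two-sided p<0.0052 at the interim and p<0.048 at the end for fraction 0.5, or 0.014 and 0.045 for 0.67. Use alpha-spending if the fraction may differ. Pocock at p<0.029 for both looks also controls the error.
2. Alternatively, state that the interim is for safety only and that no p-value stops the trial.
3. If other outcomes may trigger a stop for significance, list them and include them in the error control.
4. Leave the separate adverse-event sentence in 18.E as it is.
5. Reconcile the groups in 18.B with the Air and CO₂ groups in 12.C.

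The cost is protocol wording. Maximum enrolment stays at 200 randomized. At 38 then 75 per arm, O'Brien-Fleming gives up 0.3 points of power against a single look (81.0% against 81.3%) and 2.3 points against p<.05 at both looks (83.3%). The real price is fewer early stops and so a larger expected enrolment, by about 30 patients if the true difference is 2 mmHg. Pocock keeps more early stopping, but its power of 77.1% is below the planned 80%.
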